4. STATISTICS AND METHODOLOGY

4.1. Statistical analysis plan

In this project the null-hypothesis for the primary endpoint is the following: There is no significant reduction in biological age compared to chronological age after 6 months of collagen activator supplementation. The alternative hypothesis is the following: There is a significant reduction in biological age compared to chronological age after 6 months of collagen activator supplementation. To determine the sample size, the following power analysis was conducted using the "pwr" package in R for a one-sided hypothesis: The power of the test is set at 0.8, the significance level is set at 0.05 and the effect size at 0.5. This results in a sample size of n=50. This was then adjusted for an estimated drop-out rate of 15-20%, which results in a sample size of n=59-63. Therefore, we set the sample size at n=60.

To accommodate the inclusion of sex as a covariate in the statistical analysis, the primary endpoint analysis will employ a linear regression model. The model will include the following variables:

- Biological age reduction as the dependent variable.
- Chronological age as a covariate to account for its potential influence.
- Sex as a categorical covariate to control for the effects of gender.

The analysis will utilize the "Im" function in R's "stats" package. The significance level will be set at 0.05 (one-sided). Effect size will be calculated using Cohen's d. To correct for multiple testing, the p values will be adjusted with the Benjamin-Hochberg procedure.

Secondary endpoints within this study will be subjected to similar analysis procedures, employing linear regression models that incorporate sex as a covariate, while retaining the paired t-test structure for comparing pre- and post-intervention results.

In conclusion, the inclusion of sex as a covariate in the analysis allows us to control for its effects without altering the originally determined sample size. This approach enhances the accuracy of our analysis by considering potential sex-based variations in the primary endpoint while adhering to rigorous statistical practices.

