2.1 Hypothesis and primary objective

Primary objective: Intake of the collagen activator from Avea for 6 months will result in a significant decrease in biological age compared to the baseline.

Secondary objective: Intake of the collagen activator from Avea will lead to a significant improvement in skin quality and texture, including increased hydration, elasticity, and reduction in wrinkles, pigmentation, texture, UV-spots, pores, redness, and porphyrins after 3 months compared to baseline.

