2.2 Primary and secondary endpoints

The primary endpoint of our trial is to assess changes in DNA methylation patterns as a biomarker of biological age after the intake of the collagen activator from Avea for 6 months. Epigenetic clocks, based on DNA methylation patterns, have been shown to be associated with various health outcomes such as mortality, cardiovascular disease, cancer, diabetes, and higher BMI in several studies including Lau et al., McCrory et al., Föhr et al., Oblack et al., and Lo et al.^{13,16-17,37}.

Therefore, the rationale for using DNA methylation patterns as a biomarker of biological age is to investigate whether the intervention with the collagen activator can slow down the accelerated epigenetic clocks and potentially reduce the risk of age-related health conditions. Previous intervention studies using epigenetic clocks have shown promising results in reducing biological age through dietary and lifestyle interventions, alpha-ketoglutarate, and other lifestyle interventions, as demonstrated by Fitzgerald et al., Demidenko et al., Duan et al., Fiorito et al., and Pavanello et al.

In addition, our trial aims to establish the correlation between epigenetic clocks and relevant skin health measures. To control for potential baseline factors that might influence the outcome, we will consider factors such as gender, age, chronic diseases and smoking. By investigating changes in DNA methylation patterns, our trial will provide valuable insights into the efficacy of the collagen activator in improving cellular and tissue health and potentially reducing the risk of age-related health conditions.

Secondary endpoints:

- Hydration (measured with the corneometer): Baseline factors we consider that can influence hydration levels are age, gender, and skin type. Adequate hydration is important for maintaining skin health and preventing dryness and roughness.
- Elasticity (measured with the cutometer): Baseline factors we consider that can influence skin elasticity are age, sun exposure, and smoking. Good skin elasticity is a sign of healthy, youthful skin.
- Skin thickness and density (measured with the ultrascan): Baseline factors we consider that can lead to thinning of the skin are age and sun exposure. Measuring skin thickness and density can help determine the overall health of the skin.

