2.3 Project design

The study is a human research study in which customers that are taking the collagen activator from Avea are observed for six months. The trial is in the form of a post marketing surveillance observational trial since the product has already been approved and is sold on the market. All participants are voluntarily taking the collagen activator. There is no blinding, randomization or placebo control that is taking place in the trial. The results are compared individually for each participant after the follow ups from their baseline measurements.

- The trial exposure is the Collagen activator from Avea
 - Potential participants are contacted after purchasing the collagen activator for 6 months via Avea's online shop. After successful recruitment they undergo the baseline assessment. They are instructed to only start taking the collagen activator once the baseline assessment is completed.
 - o Daily oral intake of 1 package of 11.5g diluted in water over six months, taken in the morning
- Saliva samples are taken twice (time points 0 and +6 months) to determine biological age via epigenetic methylation clock (Trume labs are the test providers and analysers)
- Skin analysis takes place at time points 0, +1 and +3 months to determine skin quality. This includes measurements of hydration, elasticity, skin thickness and density, as well as pigmentation, wrinkles, texture, UV-spots, pores, redness and porphyrins.
- Skin tests used for this are the corneometer, cutometer, ultrascan and Visia scan.
- Every month the participants receive a questionnaire regarding recent subjective changes, adverse reactions and adherence

The individual duration expected for each patient from the recruitment process onwards is about 6-7 months

- The goal is to recruit 60 healthy participants that are older than 35 years and are voluntarily taking the collagen activator for 6 months
- 2-3 weeks from being recruited to receiving a date for the baseline measurements
- Day 1 being the day of the baseline measurements
- Follow ups for the skin measurements take place +1 and +3 months from day 1
- Follow up for the saliva test takes place +6 months from day 1

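### The primary objective compares biological age with baseline, the hypotheses compare it with chronological age, and the model's outcome has no stated reference

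*Protocol*

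**What the plan says.** - **Protocol 2.1, primary objective:** "Intake of the collagen activator from Avea for 6 months will result in a significant decrease in biological age compared to the baseline".
- **Protocol 2.2, primary endpoint:** to "assess changes in DNA methylation patterns as a biomarker of biological age after the intake of the collagen activator from Avea for 6 months". No comparator or formula is given. The rationale that follows speaks of slowing accelerated clocks and also cites studies in which biological age fell.
- **Protocol 2.3, design:** there is no control group. "The results are compared individually for each participant after the follow ups from their baseline measurements". This sentence covers all measurements, skin included. Saliva is sampled at month 0 and month 6.
- **Protocol 4.1, null hypothesis:** "There is no significant reduction in biological age compared to chronological age after 6 months of collagen activator supplementation".
- **Protocol 4.1, alternative hypothesis:** "There is a significant reduction in biological age compared to chronological age after 6 months of collagen activator supplementation".
- **Protocol 4.1, model:** "Biological age reduction as the dependent variable", without saying from what. "Chronological age as a covariate to account for its potential influence"; sex is the other covariate. The test is one-sided at 0.05.

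No section defines an age gap or age acceleration, and none reconciles the two comparators.

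**The concern.** The objective asks whether biological age falls below its starting value. The hypotheses ask whether it is reduced relative to actual age, which itself rises by half a year between the two samples. These are different questions, and the document does not say which one the primary test answers. Entering chronological age as a covariate does not settle it, because a covariate adjusts the outcome and does not supply the reference from which a reduction is measured.

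The study is open-label and uncontrolled, and it is funded by the company that sells the product. With two primary nulls on paper, the contrast could be chosen after the data are seen. A finding that participants aged more slowly than the calendar could be reported as the decrease that 2.1 promises. An unseen SAP could not cure this, since it would have to contradict one section of the protocol or the other.

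**Working it through.** **Inputs.** From 4.1: one-sided alpha 0.05, power 0.8, effect size 0.5, n=50 evaluable. From 2.3: samples at 0 and 6 months, so elapsed time is 0.5 year. The SD of the change in biological age is not given; values of 1 to 8 years are assumed below.

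**The plan's own figure.** With the noncentral t, a two-sample one-sided test at these inputs needs 50.15 per group (50 by the normal approximation), which matches n=50. A within-person one-sided test needs 26.1, so 27. Dropout inflation also reproduces: 50/0.85 = 59 and 50/0.80 = 63. The effect size is standardised, so the calculation does not show which comparator was meant.

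**The contrasts.** Let B0 and B6 be biological age at baseline and month 6, C0 and C6 chronological age, with C6 = C0 + 0.5.

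- Objective (2.1): mean(B6 − B0) < 0.
- Hypothesis (4.1), reading (i), change in the age gap: (B6 − C6) − (B0 − C0) = (B6 − B0) − 0.5, so the alternative is mean(B6 − B0) < +0.5.
- Hypothesis (4.1), reading (ii), level at month 6: B6 − C6 = (B6 − B0) + (B0 − C0) − 0.5, so the alternative is mean(B6 − C6) < 0. This contains the baseline gap B0 − C0.

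**Reading (i).** The standard error is SD/√50 and the critical t on 49 df is 1.677. The baseline test is significant when the mean change is at or below −1.677 × SE, the elapsed-time test when it is at or below 0.5 − 1.677 × SE. The last two columns give the probability of rejection when the true mean change is zero.

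| Assumed SD (years) | 0.5/SE | Threshold, baseline | Threshold, elapsed time | Rejects, baseline | Rejects, elapsed time |
|---|---|---|---|---|---|
| 1 | 3.54 | −0.24 | +0.26 | 5% | 97% |
| 2 | 1.77 | −0.47 | +0.03 | 5% | 54% |
| 3 | 1.18 | −0.71 | −0.21 | 5% | 31% |
| 5 | 0.71 | −1.19 | −0.69 | 5% | 17% |
| 8 | 0.44 | −1.90 | −1.40 | 5% | 11% |

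The elapsed-time threshold is always 0.5 year higher, so every result significant against baseline is also significant against elapsed time. Disagreement runs one way only. At an SD of 2 years or less, the elapsed-time test can succeed with no observed fall at all.

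**Reading (ii).** Assume an SD of 3 to 8 years for the month-6 gap and 2 to 4 years for the change.

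- Clock 5 years above the calendar at baseline, true fall 2 years: mean(B6 − C6) = 5 − 2 − 0.5 = +2.5. The baseline test rejects in 97–100% of trials, the level test in under 0.1%.
- Clock 3 years below the calendar at baseline, no change: mean(B6 − C6) = −3 + 0 − 0.5 = −3.5. The baseline test rejects in 5%, the level test in 92–100%.

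Here disagreement runs both ways. The second case succeeds on the clock's calibration in this cohort alone.

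**The case against.** Several points on the other side have force.

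- **The document leans to baseline.** The objective is explicit, 2.3 compares participants with their own baseline, and 4.1 keeps a paired pre/post structure for the secondary endpoints. This stands as a hint about intent. It does not override formal hypotheses that twice name another comparator. Nor should 2.3 be read as a success criterion: it describes how results are compared and sets no threshold.
- **The model may fit a chronological-age reading.** One might infer that it fits none of them. The text does not support that: the outcome is undefined and could be a reduction in the age gap, and even as baseline minus month 6, reading (i) is the same model with its null shifted by 0.5 year.
- **A rejection with flat biological age is not a false positive for the elapsed-time null.** This is right: if biological age stands still for six months, ageing was slower than the calendar. The harm arises only if that result is reported as a decrease.
- **The elapsed-time contrast has its own support.** The rationale in 2.2 is partly about slowing the clock. If an untreated clock advances with the calendar (an assumption), elapsed time is the no-effect null, and the baseline test would reject in only about 0.25% of trials with no effect at an SD of 3 years. This stands, and makes the choice one for the sponsor to declare.
- **At the planned effect the tests seldom disagree.** With a true fall of 0.5 SD, n=50 and an SD of 3 years, the baseline test rejects in 97% and the elapsed-time test in over 99% of trials, about 3 points apart. This is also right, but the hypothesis must be fixed for smaller effects too.

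**Conclusion.** The conflict is in the wording of the protocol and needs correction before analysis: 2.1 and 4.1 name different comparators, and the outcome has no reference. That conclusion needs no assumption.

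Its size does. A reader might infer that the two nulls are always half a year apart and can give opposite verdicts. The documents support less. The half-year holds only under the change-in-gap reading, and there disagreement means significant against elapsed time but not against baseline, never the reverse. Under the level reading the difference is the baseline gap less 0.5 year, which may be much larger, and either test can succeed alone.

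The rejection rates of 54%, 31% and 17% (97% at an SD of 1 year, 11% at 8) against 5% are illustrations. They rest on assumed SDs, n=50, a common interval of exactly 0.5 year and a simple within-person t-test without covariates. Section 6.2 allows a spoiled sample to be retaken within 1 to 1.5 months, so the true interval will vary somewhat.

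**What to change.** Name one contrast in 2.1, 2.2 and 4.1, and define biological age reduction by formula.

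- **Matching the stated primary objective:** H0: mean(month-6 minus baseline biological age) ≥ 0 against H1: < 0. Keep the change minus the elapsed time between each participant's two samples as a named supportive analysis, which serves the slowing rationale in 2.2.
- **If the sponsor prefers elapsed time as primary:** reword the objective and the permitted conclusion to slower biological ageing, and make no claim of a decrease from that test.
- **In either case:** do not use month-6 biological age against chronological age as a test of effect.

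The cost is protocol wording, with ethics committee approval if the change counts as substantial under 5.5. No participants, visits or samples are added. Of the two change-based tests, the baseline contrast is the more demanding.

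### The primary regression names no tested parameter, and none of its coefficients as listed is the mean reduction in biological age that the hypothesis concerns

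*Protocol*

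**What the plan says.** Protocol section 4.1, itself titled as the statistical analysis plan, gives the primary null hypothesis as "There is no significant reduction in biological age compared to chronological age after 6 months of collagen activator supplementation". It then fixes the analysis: "To accommodate the inclusion of sex as a covariate in the statistical analysis, the primary endpoint analysis will employ a linear regression model". Three elements are listed:

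- Outcome: "Biological age reduction as the dependent variable"
- First covariate: "Chronological age as a covariate to account for its potential influence"
- Second covariate: "Sex as a categorical covariate to control for the effects of gender"

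R's lm is the function and the level is 0.05, one-sided. The section closes by saying that including sex "allows us to control for its effects without altering the originally determined sample size".

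Section 2.3 describes the design: "There is no blinding, randomization or placebo control that is taking place in the trial", and "The results are compared individually for each participant after the follow ups from their baseline measurements". Section 3.1 sets the minimum age at 35.

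No coefficient or contrast is named as the primary test. No centring of age, coding of sex or adjusted mean is mentioned. A paired t-test is said to be kept, but that sentence concerns the secondary endpoints.

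**The concern.** The hypothesis is about a mean: is biological age lower, on average, after six months? In a randomised trial a regression with covariates still has a treatment coefficient to carry the test. Here everyone is exposed, so once age and sex are in the model only the age slope, the sex difference and the intercept remain. The first two say how change varies between people. The third is a mean change, but at covariate values of zero, which for age lies 35 years below the youngest eligible participant.

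An analyst who fits the listed model therefore finds no p value in the default output that answers the primary question. The analyst must either take the wrong one or choose a contrast after seeing the data. The sole primary conclusion depends on that choice.

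**Working it through.** **The model as listed.** E[reduction] = b0 + b1·age + b2·sex.

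- b1: difference in reduction per year of age.
- b2: difference in reduction between the sexes.
- b0: expected reduction at age 0 in the reference sex (lm's default, with age in years).

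If age and sex are each centred at their sample means, b0 becomes exactly the sample mean reduction.

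**Inputs from section 4.1.** One-sided 0.05, effect size 0.5, evaluable n=50, target power 0.8. The drop-out inflation reproduces: 50/0.85 = 58.8, so 59; 50/0.80 = 62.5, so 63. The 50 reproduces only as the per-group size of a one-sided two-sample t-test (50.15). A one-sided paired test on the same inputs needs 27. That is a separate matter, but it explains why the reference power below is well above 80%.

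**Assumptions, not in the protocol.** Residual SD 1; mean age 45 to 55 with SD 7 to 10; 80% of participants in the reference sex; age and sex uncorrelated.

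**Reference power.** For a paired t-test with n=50 and d=0.5, the noncentrality is 0.5·√50 = 3.54 on 49 df, so power is 0.967. The centred regression intercept has the same noncentrality on 47 df, and its power is also 0.967.

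**Default intercept: standard error.** With p the share in the non-reference sex, the SE relative to that of the mean change is approximately

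k = √(1 + (mean age/SD)² + p/(1−p)), with p = 0.2.

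The noncentrality falls to 3.54/k.

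| Mean age / SD | k | 3.54/k | Power, formula | Power, simulated (5,000 runs) |
|---|---|---|---|---|
| 45 / 7 | 6.53 | 0.54 | 0.13 | 0.123 |
| 50 / 8 | 6.35 | 0.56 | 0.14 | 0.138 |
| 50 / 10 | 5.12 | 0.69 | 0.17 | 0.147 |
| 55 / 10 | 5.61 | 0.63 | 0.15 | 0.150 |

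Restricting ages to 35 or older narrows their spread, so the simulated SE ratios are a little larger (5.6 to 7.2) and power is mostly a little lower than the formula gives. Repeat runs with other sex mixes and age spreads gave 0.11 to 0.16. The centred intercept and the paired t-test gave 0.96 to 0.97 throughout.

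**Default intercept: type I error.** Suppose the mean reduction is zero but reduction changes by g SD per year of age. The expected intercept is then −g × mean age. At mean age 50, g = −0.01 gives 0.5 SD, as large as the planned effect; g = −0.02 gives 1.0 SD. Rejection rates at nominal 5% (age 50, SD 8):

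| g (SD per year) | Default intercept | Centred intercept |
|---|---|---|
| −0.02 | 26–28% | about 5% |
| −0.01 | about 13% | about 5% |
| 0 | about 5% | about 5% |
| +0.01 | about 1–2% | about 5% |
| +0.02 | under 1% | about 5% |

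The power loss needs no age slope; extrapolation to age 0 alone produces it. The distortion of type I error needs a slope, and its direction follows the slope's sign.

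**The case against.** The strongest reply is that section 4.1 never says the default intercept is the test. It lists variables and software, and a competent analyst would centre the covariates or report an adjusted mean. That much stands: a reader might infer that the primary test, run as written, loses nearly all its power, but the protocol does not support this because it names no tested parameter. The power and error figures show what one unstated choice would cost.

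It may also be said that such detail belongs in a separate analysis plan. Ordinarily it would. Here the section is headed as the analysis plan and fixes the outcome, covariates, function and level. The objection is to the model it fixes, whose default output does not contain the answer.

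Three further inferences are tempting and should not be drawn:

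- **That the sample-size sentence is false.** It fails only if the default intercept is tested. With centred covariates the cost is two degrees of freedom, and power at n=50 stays near 97%.
- **That the secondary tests are lost too.** Section 4.1 keeps a paired pre/post comparison for them. The wording does not explain how that fits with a sex covariate, but the mean-change test is named.
- **That the false-positive rate is inflated.** The documents give no age slope. A negative slope inflates the rate; a positive one makes the test conservative.

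Nor are the covariates useless. Age and sex do not confound a within-person mean change, and the centred intercept equals the unadjusted mean. They can still reduce residual variance and describe who changes more.

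**Conclusion.** The point holds in this form: section 4.1 replaces the primary test with a single-arm regression, leaves the tested parameter unnamed, and lists a model in which no coefficient is the mean reduction. That follows from the text alone and needs no assumption about ages.

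The size is conditional. If lm's default intercept were taken as the test, power at n=50 and 0.5 SD would be about 12 to 15% against about 97%. Its rejection rate under a zero mean change would run from about 1–2% to 26–28% for slopes between +0.01 and −0.02 SD per year. These figures rest on assumed ages, sex mix and slopes.

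The target quantity is also unsettled. Section 2.1 measures the decrease against baseline, while the hypotheses in 4.1 measure it against chronological age. Over six months the two differ by about half a year, so naming the parameter also means choosing between them. The primary test should be settled before any month-6 result is seen.

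**What to change.** In section 4.1:

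1. State that the tested parameter is the mean within-person change from baseline to month 6. Test it with a one-sided one-sample (paired) t-test and give its confidence interval. Alternatively, use the intercept of the linear model with age and the sex indicator both centred at their sample means. The point estimate is the same; the residual variance and degrees of freedom differ slightly. Choose one as primary.
2. Say whether the change is in biological age itself (section 2.1) or in biological age relative to chronological age (the hypotheses in 4.1), and align the two sections.
3. Report the age and sex coefficients as descriptive.
4. For the secondary endpoints, state that the retained paired comparison is the test and that any sex term is centred.

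The cost is one paragraph in 4.1 and one aligned sentence in the objective or hypotheses. Enrolment, visits and data collection do not change.

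### Protocol section 4.1 tests the primary endpoint one-sided at 0.05 without a stated reason, which doubles the chance of a false benefit claim relative to a two-sided 5% test and leaves a rise in biological age untestable; the side of the skin tests is not stated

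*Protocol*

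**What the plan says.** Protocol section 4.1 frames the primary alternative as a reduction in biological age only and sizes the study for a one-sided hypothesis. The inputs are: "The power of the test is set at 0.8, the significance level is set at 0.05 and the effect size at 0.5". The result is: "This results in a sample size of n=50". This is raised to 59-63 for drop-out of 15-20% and set at 60. The primary analysis is a linear regression with chronological age and sex as covariates, and "The significance level will be set at 0.05 (one-sided"). The p values are then adjusted by the Benjamini-Hochberg procedure.

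For the skin measures, section 4.1 says: "Secondary endpoints within this study will be subjected to similar analysis procedures". It goes on to mention regression with sex as a covariate and a paired structure. It gives no separate level or side for them.

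The secondary objective in section 2.1 is directional: "including increased hydration, elasticity, and reduction in wrinkles, pigmentation, texture, UV-spots, pores, redness, and porphyrins after 3 months compared to baseline". Section 2.2 also lists as an endpoint "Skin thickness and density (measured with the ultrascan"), which the objective does not name.

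On the design, section 2.3 says "The trial is in the form of a post marketing surveillance observational trial", without randomisation, blinding or placebo. Each participant is compared with their own baseline.

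**The concern.** A one-sided level of 0.05 is a lenient threshold for a claim of benefit. The conventional two-sided 5% test allows 2.5% in the favourable direction, and this plan allows twice that.

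The setting makes leniency harder to defend. There is no control group. The sponsor sells the product and funds the study (section 8). Section 7.3 states the hope of repeating a large reduction reported earlier with the same test. A result could be called significant while the two-sided 95% confidence interval for the mean change still includes zero.

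The second cost is that the formal test cannot declare a rise in biological age, however large, in a study presented as post-marketing surveillance.

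The third is ambiguity. A reader of section 4.1 cannot tell whether the skin endpoints are tested one-sided. If they are, section 2.1 does not say which side applies to thickness and density.

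**Working it through.** **Inputs.** All are from protocol section 4.1: one-sided level 0.05, power 0.8, effect size 0.5, 50 evaluable, drop-out 15-20%, 60 recruited. The protocol does not say which SD the effect size refers to. I take it as the SD of the within-person change, which is an assumption.

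**1. The plan's own figure.**
- The normal-approximation formula for two independent groups, one-sided, is n per group = 2 × (1.645 + 0.842)² / 0.5² = 49.5, rounded up to 50. The t-based version gives 50.15.
- Inflation: 50/0.85 = 58.8, so 59; 50/0.80 = 62.5, so 63. Both match the protocol.
- Of the variants tried, only this one gives 50, and it is a per-group number for a two-group test. For a one-group change the t-based requirement is 26.14, so 27 completers one-sided, and 33.37, so 34 two-sided. The two-group two-sided version needs 64 per group.

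**2. Error rate for a benefit claim**, before multiplicity adjustment.
- One-sided 0.05: 5%.
- Two-sided 0.05: 0.05/2 = 2.5%.

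**3. What the threshold means with 50 completers (49 df).**
- Critical t: 1.677 one-sided, 2.010 two-sided.
- Smallest significant mean change: 1.677/√50 = 0.237 SD against 2.010/√50 = 0.284 SD.
- If the true change were a worsening of 0.5 SD, the one-sided test would reject with probability of about 1 in 10 million (normal tail beyond 1.645 + 0.5 × √50 = 5.18), and then only for benefit.

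**4. Power for a one-group change** (noncentral t, noncentrality = d × √n). The 48 completers are 60 × 0.80, 50 is the protocol's own figure, and 51 is 60 × 0.85.

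| Completers | d | One-sided 0.05 | Two-sided 0.05 |
|---|---|---|---|
| 48 | 0.5 | 96.2% | 92.4% |
| 50 | 0.5 | 96.7% | 93.4% |
| 51 | 0.5 | 97.0% | 93.8% |
| 50 | 0.4 | 87.4% | 79.2% |
| 50 | 0.3 | 67.3% | 54.8% |

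Taking off two further degrees of freedom for the covariates leaves 93.4% at 50 completers unchanged to one decimal. At the protocol's effect size the loss is 3.3 points with 50 completers and 3.8 with 48. It is larger if the true effect is smaller.

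**5. Role of the Benjamini-Hochberg adjustment.** The family is not defined. Suppose it is the primary plus the eleven skin measures, twelve in all (my assumption). The sixth-ranked threshold is 6/12 × 0.05 = 0.025. A primary p value above 0.025 is then declared significant only if at least seven of the twelve, itself included, are rejected. The adjustment can therefore remove some borderline results. It does not undo the choice of side, because a favourable one-sided p is half the two-sided p before it enters the procedure.

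**6. Direction of the skin endpoints.** Section 2.1 gives a direction for hydration, elasticity and the seven Visia measures. Thickness and density appear in section 2.2 but not in that list.

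**The case against.** The strongest reply is that the one-sided choice is prespecified and consistent. Objective, alternative hypothesis, power analysis and analysis level all point to a reduction, and the test holds its declared 5%. That stands: there is no contradiction on the side of the primary test and no inflation beyond the declared level. What is missing is a reason for 5% rather than 2.5% in a study without a control group.

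Several stronger readings are tempting, but the protocol does not support them.

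- **That the skin tests are one-sided.** Section 4.1 does not say so. The similarity it spells out is regression with sex and a paired structure. A separate SAP, not at hand, could fix the side.
- **That every t between 1.68 and 2.01 will be reported as a significant reduction.** This ignores the Benjamini-Hochberg adjustment. It would hold only if the primary p value were left unadjusted, which the protocol does not say.
- **That worsening can never be shown.** This is true only of the rejection region. Regression coefficients and Cohen's d carry a sign, and adverse reactions are collected monthly.
- **That thickness and density carry a real error rate of 10%.** That needs the side to be picked after the data are seen, and nothing provides for it. The list in 2.1 is not worded as exhaustive, and the background in section 1 treats thinning as ageing and greater thickness as improvement. Density is less clear.

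It is also fair that a two-sided test does not repair the lack of a control group.

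**Conclusion.** The point holds for the primary endpoint: an unjustified one-sided 0.05 level doubles the unadjusted chance of a false benefit claim (5% against 2.5%) and leaves no formal test for a rise. For the skin endpoints it is conditional. The side is unstated, and only if the one-sided level carries over does the absence of thickness and density from section 2.1 leave their tests without a direction.

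The practical size is modest: the threshold moves from 0.237 to 0.284 SD at 50 completers. The change is still worth making, because on a one-group change the planned 60 participants support the stricter test with power of about 92 to 93% at 48 to 50 completers. That rests on an effect of 0.5 in SDs of the change; at 0.4, power with 50 completers is 79.2%.

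**What to change.** - In section 4.1, replace the one-sided level by a two-sided 0.05 test (equivalently one-sided 0.025 for a claim of benefit), with two-sided 95% confidence intervals, for the primary and for all skin endpoints. Keep the Benjamini-Hochberg adjustment.
- In section 2.1, add skin thickness and density to the secondary objective.
- Restate the sample-size sentence for a one-group change at two-sided 0.05. The printed 50 matches only the one-sided two-group formula and would lose its basis if the side alone were changed. At an effect of 0.5 SD of the change, 80% power needs 34 completers, or 34/0.85 = 40 to 34/0.80 = 42.5 (43) recruited. The planned 60 can stay.

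The cost is an edit to sections 2.1 and 4.1 and about 3 to 4 percentage points of power at the stated effect size. No extra participants, visits or measurements are needed.
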